1.3. Benefit/Risk Aspects

Subjects in this study may benefit from being treated with imlifidase to resolve early graft rejection. The potential benefit of imlifidase compared to currently used methods, e.g. PE, is the efficacious and immediate removal of DSAs. It is anticipated that a faster DSA removal will result in less damage to the allograft and thus a better outcome for the patient. If imlifidase fails to remove DSAs to satisfactory levels or if the DSAs rebound, the patient will be treated with PE and/or other standard of care (SOC) treatments, as judged by the investigator. SOC treatment can be initiated at any point for patients in the treatment arm if needed. The decision to initiate other SOC treatments will normally be based on DSA rebound. Since DSA is monitored frequently, signs of antibody rebound will be detected early and appropriate treatment initiated immediately. Thus, it is anticipated that there will be no risk that the patient does not receive the best available treatment.

Since imlifidase effectively removes the IgG pool, there may be an increased risk of infection. To minimize the risk for bacterial infections all subjects included in the study will receive prophylactic antibiotics. Subjects will be closely monitored for infections and instructed to contact the principal investigator immediately if they have any sign of infection. There will be a physician specialized in infectious diseases available for medical advice in case of a patient showing signs of infection. In case of infection in a patient with low IgG plasma levels, intravenous immunoglobulin may be indicated. Subjects will be screened for SARS-CoV-2 and subjects with a positive test will not be included in the study. As SARS-CoV-2-naïve subjects

do not have any IgG antibodies towards the virus, and since imlifidase does not prevent IgG synthesis, administration of imlifidase is not considered to have any impact on patient safety should the subject subsequently become infected with SARS-CoV-2.

Although samples for analysis of ADA will be taken at screening, it is not possible to wait for the sample to be analyzed before inclusion in the study as this would delay the treatment and thus have a serious impact on patient outcome.

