3. INVESTIGATIONAL PLAN

3.1. Overall Study Design

This is a randomized, open label, multi-centre, study with an active control. The study will primarily examine the reduction in mean levels of DSA after treatment with imlifidase compared to PE in patients diagnosed with active or chronic active AMR according to Banff 2017 criteria (Haas et al. 2018), including presence of DSA(s). A total of 30 male and/or female patients will be included in the study.

The randomization will be 2:1. 20 subjects will receive a single dose of 0.25 mg/kg imlifidase and 10 subjects will be treated with 5-10 sessions of PEs. High dose IVIg followed by a single dose of rituximab will be given after treatments with imlifidase and PE. For doses, see Section 5. Other treatments and/or procedures for AMR can be used as required at the investigator’s discretion. SOC treatment can be initiated at any point for patients in the treatment arm if needed as judged by the investigator. The decision to initiate other SOC treatments will normally be based on DSA rebound. Since DSA is monitored frequently, signs of antibody rebound will be detected early and appropriate treatment initiated immediately.

The duration of the hospitalization for subjects in the imlifidase arm will be at least 2 days. In the control arm, the duration of the hospital stay will follow standard of care at each study site.

Presence of DSA will be assessed pre-dose and at multiple times during the study. Protocol biopsies will be performed at screening, and on day 29 and day 180 after first day of treatment to assess changes in allograft histopathology and mRNA levels. . If kidney biopsy is performed within 5 days prior to screening it will not have to be repeated at screening visit and mRNA levels will be measured on day 29 and day 180. In addition, kidney function will be followed by plasma or serum creatinine measurements, eGFR calculations and albumin/creatinine ratio in urine during the full study period.

The study outline is summarized in Figure 1 (imlifidase) and Figure 2 (PE) below.

Figure 1: Overall study outline imlifidase arm

[figure not shown]
[figure not shown]

Figure 2: Overall study outline PE arm

Safety parameters (safety laboratory tests, vital signs and ECG) as well as kidney function and AEs will be monitored up to 180 days after start of treatment.

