5.3. Non-Investigational Medicinal Product(s)

Non-Investigational Medicinal Products (NIMPs) will be sourced from the investigational site pharmacy supply. Essential information about the NIMPs is to be found in the latest versions of respective Summary of Product Characteristics.

The subjects will be treated with the following NIMPs (other treatments may be used as required at the investigator's discretion):

Prophylactic antibiotic (all subjects):

All subjects will receive a standard regimen of antibiotics according to local clinical practice, starting before the first treatment and continuing until IgG levels return to acceptable values, as judged by the investigator.

Premedication (imlifidase arm):

All subjects in the imlifidase arm, will be given antihistamine (orally) as pretreatment before imlifidase infusion.

Treatment schedule for steroid dosing (all subjects):

Day 1: Methylprednisolone 500 mg as premedication before treatment
Day 2-3: Methylprednisolone 500 mg daily
Day 4: Prednisolone/prednisone 60 mg
Day 5: Prednisolone/prednisone 50 mg
Day 6: Prednisolone/prednisone 40 mg
Day 7: Prednisolone/prednisone 30 mg
Day 8: Prednisolone/prednisone 20 mg will continue daily for 1 week, followed by 10 mg daily for 1 week and thereafter 5 mg daily throughout the study

Treatment with IVIg (all subjects)

Imlifidase arm: subjects will be given a high dose of IVIg (2 g/kg BW, maximum of 140 g), on day 4 (may be given over 2 days, as judged by the investigator). If a subject in this arm has to be treated with PE for medical reasons, IVIg will be given after the last session of PE.

PE arm: a high dose of IVIg (2 g/kg BW, maximum of 140 g) will be given after the last session of PE (may be given over 2 days, as judged by the investigator).

Treatment with Rituximab (all subjects)

A single dose of rituximab, 375 mg/m², will be given to all subjects 5 days after completion of the IVIg infusion.

Rituximab requires use of contraception for 12 months after treatment. Women of childbearing potential will be encouraged to continue using highly effective contraceptive method for at least 6 months after end of study.

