12.3. Statistical Analysis of Endpoints

12.3.1. Primary efficacy endpoint

The primary endpoint is the maximum reduction in DSA (MFI sum for relevant DSAs) at any time point during the 5 days following the start of treatment. A subject will have at least one DSA and a DSA is considered relevant if it is at least 1000 MFI pre-dose. The reduction is derived as follows:

- 1) Calculate the reduction (%) in sum of DSAs as $100 \times (DSA_0 - DSA_t) / DSA_0$ for each subject and time point. Only DSAs with a pre-dose MFI of 1000 or more will be included in the calculations
- 2) Find the time point with maximum reduction within 5 days for each subject
- 3) The maximum reduction per subject will give a single value as the primary endpoint for the subject

Where DSA_t is the analysis result in total MFI for relevant DSAs at time t.

Due to the exploratory nature of this study, no formal hypothesis will be tested. The difference in reduction between the two treatments will be presented with 95% CI. Each subject will be given equal weight in the calculation of the treatment difference irrespective of number of DSAs for the subjects.

A summary table showing the proportion of reduction of DSAs calculated per subject will also be presented.

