3.1 Full Analysis Set

FAS will consist of all patients treated with any amount of study medication. Patients will contribute to the analysis ‘as randomized’.

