4.6 Efficacy

4.6.1 Primary efficacy analysis

The primary endpoint is the maximum reduction in DSA at any time point during 5 days following start of treatment. No formal statistical hypothesis will be tested for the primary endpoint. The FAS and PPS set will both be used for the primary endpoint. The primary endpoint will be calculated as part of the ADaM programming.

The DSAs are given as levels of mean fluorescence intensity (MFI) and genetic region of interest. These parameters are used to calculate the reduction in DSA for individual patients in the following steps:

- 1) Determine the DSAs having MFI levels larger than or equal to 1000 at baseline for the considered patient. Calculate DSA_0 as the sum of these MFI levels.
- 2) Calculate DSA_t for each patient as the sum of the MFI levels for the time point t , using the DSAs from step 1.
- 3) The reduction (%) is calculated as $100 \times (DSA_0 - DSA_t) / DSA_0$ for each patient and time point. In the formula DSA_t is the total MFI level at time t .
- 4) The time point with maximum reduction within 5 days is found and chosen for each patient.

- 5) The maximum reduction per patient is a single value as the primary endpoint for the patient.

The difference in reduction between the two treatments will be presented with 95% CI in a table. The confidence interval for the difference in the reduction is found by using an Analysis of variance (ANOVA) model with treatment as fixed effect.

The reduction of DSAs calculated per patient will also be presented in a summary table by treatment and visit and presented in a mean plot by treatment and time point. The maximum reduction per patient will be listed by patient.

If the normality assumption is violated, sensitivity analyses using transformations of the primary endpoint will be performed.

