14.1.7	Table	Exposure (FAS)
EFFICACY DATA		
14.2.1	Table	Difference in maximum DSA reduction and 95% CI (FAS)
14.2.2	Table	Difference in maximum DSA reduction and 95% CI (PPS)
14.2.3	Table	DSA reduction - by time point (FAS)
14.2.4	Table	DSA reduction - by time point (PPS)
14.2.5	Table	MFI levels for DSA c1q - by time point (FAS)
14.2.6	Table	Proportion of patients with absence of graft loss at day 180 (FAS)
14.2.7	Table	Proportion of patients having no signs of transplant glomerulopathy at day 180 (FAS)
14.2.8	Table	Kidney biopsy (Banff) - Scores - by time point (FAS)
14.2.9	Table	Kidney biopsy (Banff) - Change from baseline (scores) - by time point (FAS)
14.2.10	Table	Kidney biopsy (Banff) - Interpretations - by time point (FAS)
14.2.11	Table	Kidney biopsy (Banff) - Shift table - by time point (FAS)
14.2.12	Table	Kidney biopsy () - Scores - by time point (FAS)
14.2.13	Table	Kidney biopsy () - Change from baseline - by time point (FAS)
14.2.14	Table	Number of sessions of PE and IA for 180 days (FAS)
14.2.15	Table	Total IgG - by time point (FAS)
14.2.16	Table	Proportion of patients having reduction in total IgG - by time point (FAS)
14.2.17	Table	Composition of IgG-fragments (SDS-PAGE) - by time point (FAS)
14.2.18	Table	Proportion of patients having no detectable intact IgG (PKS)
14.2.19	Table	Proportion of patients with resolution of AMR at day 180 (FAS)
14.2.20	Table	Patient survival at day 180 (FAS)
14.2.21	Table	Summary of imlifidase (PK) concentrations - by time point (PKS)
14.2.22	Table	Summary of imlifidase PK parameters (PKS)
DISPLAYS OF ADVERSE EVENTS		
14.3.1	Table	Overview of treatment-emergent AEs (SAF)
14.3.2	Table	Summary of treatment-emergent AEs - by SOC and PT (SAF)
14.3.3	Table	Summary of treatment-emergent AEs - by causality (SAF)

14.3.4	Table	Summary of treatment-emergent AEs - by intensity (SAF)
14.3.5	Table	Summary of related treatment-emergent AEs - by intensity (SAF)
14.3.6	Table	Summary of SAEs (SAF)
14.3.7	Table	Summary of SAEs - by causality (SAF)
14.3.8	Table	Summary of treatment-emergent SAEs (SAF)
14.3.9	Table	Summary of treatment-emergent SAEs - by causality (SAF)
14.3.10	Table	Summary of treatment-emergent SAEs leading to death (SAF)
14.3.11	Table	Summary of treatment-emergent AEs leading to withdrawal (SAF)
DISPLAYS OF SAFETY DATA		
14.4.1	Table	Summary of clinical chemistry variables - by time point (SAF)
14.4.2	Table	Summary of haematology variables - by time point (SAF)

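### The primary maximum counts imlifidase-arm samples taken after rescue plasma exchange, and no planned between-arm confidence interval is limited to pre-rescue samples

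*SAP*

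**What the plan says.** SAP 4.6.1 computes the percentage reduction in summed DSA MFI at each time point. Step 4 then reads: "The time point with maximum reduction within 5 days is found and chosen for each patient". Protocol 12.3.1 has the same rule: "Find the time point with maximum reduction within 5 days for each subject". Neither section excludes any sample because of other treatment. The arm difference and its 95% CI come from an ANOVA with treatment as the only effect, in the FAS and the PPS. The only sensitivity analysis named is a transformation if normality fails.

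Rescue in the imlifidase arm is foreseen in three places:

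- Protocol 1.3: "If imlifidase fails to remove DSAs to satisfactory levels or if the DSAs rebound, the patient will be treated with PE".
- Protocol 3.1: "SOC treatment can be initiated at any point for patients in the treatment arm if needed as judged by the investigator". The same section adds: "The decision to initiate other SOC treatments will normally be based on DSA rebound".
- Protocol 5.3, on an imlifidase-arm subject who "has to be treated with PE for medical reasons, IVIg will be given after the last session of PE". IVIg is otherwise due on day 4, so PE inside the five-day window is anticipated.

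SAP 3.1 says: "FAS will consist of all patients treated with any amount of study medication", analysed as randomized. SAP 3.2 removes major deviations from the PPS, but permitted rescue PE is not among its examples.

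SAP 8 plans DSA reduction by time point (Tables 14.2.3 and 14.2.4), individual plots (Figures 15.1.2 to 15.1.31) and listings of DSA reduction and of PE/IA sessions (16.2.1.1 and 16.2.1.9). All are descriptive.

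**The concern.** The primary objective compares imlifidase with PE in removing DSA. A maximum can only rise or stay the same when samples are added. If an imlifidase patient responds poorly and then receives PE on, say, day 3, the deepest value may be one that PE produced, and the rule credits it to imlifidase. Any such contribution moves the difference in favour of imlifidase.

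The primary analysis (FAS and PPS) is the only between-arm DSA difference with a planned CI. Where rescue occurs, it compares imlifidase with or without PE against PE. The comparison before PE was added can be read only patient by patient or from means by time point. The session summaries in SAP 4.6.2 cover 180 days, or the time after IVIg starts. Because a rescued imlifidase patient receives IVIg after the last PE, the second summary misses early rescue, and the first does not isolate the window.

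**Working it through.** **Inputs.** 20 imlifidase and 10 PE patients; SDs of 4% and 6% from two previous imlifidase studies (Protocol 12.4, SAP 2.2). Those SDs describe IgG reduction, not DSA reduction. No document gives a rescue rate or the size of a rescue effect, so k and g below are assumptions.

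**1. The plan's own figure.** Half-width = t(0.975, 28) × SD × √(1/20 + 1/10), with t = 2.048 and the root = 0.387.

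| SD | Half-width | Full width |
|---|---|---|
| 4 | 3.17 | 6.35 |
| 5 | 3.97 | 7.93 |
| 6 | 4.76 | 9.52 |

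The stated width of about 8 points is reproduced at the midpoint SD of 5.

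**2. Shift from post-rescue samples.** If k of 20 imlifidase patients each gain g points from samples after rescue, the arm mean rises by k × g/20. The shift is 0 when every maximum precedes rescue.

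**3. Width of an interval on pre-rescue samples.** Take SD 5 in both arms for the all-samples maximum, and lower k imlifidase values by g:

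- imlifidase variance v = 25 + g² × k(20 − k)/(20 × 19)
- pooled variance = (19v + 9 × 25)/28
- half-width = 2.048 × pooled SD × 0.387

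For k = 1 and g = 20: v = 25 + 400 × 19/380 = 45; pooled variance = (855 + 225)/28 = 38.6; SD = 6.21; half-width = 4.93.

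| k | g | Shift removed | Pooled SD | Half-width |
|---|---|---|---|---|
| 1 | 20 | 1.0 | 6.21 | 4.93 |
| 4 | 20 | 4.0 | 8.41 | 6.67 |
| 1 | 50 | 2.5 | 10.48 | 8.31 |
| 2 | 50 | 5.0 | 13.63 | 10.81 |

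In each case the half-width exceeds the shift removed.

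**4. Which samples are within five days.** The last DSA sample of Visit 2 (Day 1-5) is at 96 h ± 6 h; the Day 6 visit is nominally at 120 h. Protocol 6.1 also requires a PE-arm sample 24 h after the last session. With five daily sessions (0, 24, 48, 72, 96 h) that is 96 + 24 = 120 h, on the boundary. SAP 4.6.2 specifies actual sampling times for PK, but 4.6.1 is silent for DSA. Protocol 7.1.1 has standard-of-care DSA results entered in the eCRF without saying whether they count.

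To illustrate, assume each session removes a fraction r = 0.5 to 0.7 of DSA and a share b = 0.3 to 0.5 of that returns before the next session. Samples coinciding with a session are taken before it. Each daily cycle leaves c = 1 − r(1 − b), from 0.51 to 0.75. Counting Day 6 raises the PE-arm maximum by 100 × c⁴(1 − c): 3.3 points at c = 0.51 and 7.9 at c = 0.75. With alternate-day sessions the gain is 10.1 to 13.1 points if return is linear, and 5.5 to 14.8 if return is complete by 24 h. With r = 0.1 to 0.3 and no return, the gains are 6.6 to 8.2 (daily) and 8.1 to 14.7 (alternate-day).

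**The case against.** The strongest reply is that the plan does have a rule. A maximum over any time point, in patients analysed as randomized, includes post-rescue samples, and that is a recognised treatment-policy estimate. This stands. A reader might infer that the primary is invalid or must be replaced, and the documents do not support that. Nor is an error rate at stake, because no hypothesis is tested.

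Second, the exposure is narrow. It needs early non-response, then PE or IA within five days, then a deeper fall. Protocol 1.1 describes the whole IgG pool as cleaved within a few hours. On Protocol 12.4's figures (90%, SD 6; 93%, SD 4), a pre-rescue maximum of 50% lies at least (90 − 50)/6 = 6.7 SD below the mean. Those are IgG figures, so they do not rule out such a patient for DSA, but nothing in the documents supports the 50-point illustrations.

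Third, early values are already tabulated, plotted and listed, and with 20 imlifidase patients much can be read from the listings. That is true; what is missing is the between-arm interval and a direct count of rescues inside the window.

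Fourth, truncating only the imlifidase arm can lower its maxima but never raise them. A reader might take the result as the clean effect of imlifidase without PE. It is not, because a slow responder might have fallen further without rescue.

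**Conclusion.** The point holds in limited form. As written, the primary counts imlifidase-arm samples after PE/IA, so a fall caused by the comparator can be credited to imlifidase in early non-responders. No planned between-arm interval shows the difference without those samples.

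The size is unknown. It is k × g/20 points: 1.0 for one patient gaining 20, and k × g must reach about 80 (for example two patients gaining 40 each) before the shift equals the planned half-width of 4.0 at SD 5. It is zero if rescue follows rebound and the maximum came first. This is a cheap improvement in how the estimate can be read, not a correction of an invalid analysis.

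The undefined window is a minor clarification. A reader might infer a second error worth 3.3 to 14.8 points in the PE arm. Those figures rest wholly on assumed removal, return and session spacing, and are not evidence of magnitude. Visit 2 ending at 96 h is a natural reading, and central DSA analysis (Protocol 7.1.1) makes local standard-of-care results an unlikely input, but the SAP states neither.

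**What to change.** In SAP 4.6.1:

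1. Keep the all-samples maximum as the primary and state that samples count regardless of rescue PE/IA.
2. Add one pre-specified sensitivity analysis: repeat steps 1 to 5 and the same ANOVA difference with 95% CI, excluding imlifidase-arm samples taken after the first PE/IA session. Where no clock time exists, exclude a sample from the same day. A patient left with no eligible sample stays missing (SAP 4.1.4) and is counted in a footnote.
3. Report how many imlifidase patients had PE/IA within the window, and how many have their maximum at a post-PE/IA sample.
4. As an accompanying clarification, the same for both arms: state whether the window includes the Day 6 sample, whether nominal or actual time decides, and whether standard-of-care DSA results count.

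The cost is SAP wording, one interval and two counts, from samples already scheduled. No change to treatment is involved. There are three downsides:

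- The interval is wider, about 4.9 to 10.8 in the illustrations against 4.0 planned, so it must be read beside the primary and the counts, not in place of them.
- With one arm truncated, it is a conservative bound. For the arm mean, that holds only while no rescued patient drops out for lack of an eligible sample, hence the footnote.
- Protocol 5.7 and SAP 4.5 provide dates rather than clock times for PE, so the same-day rule may discard true pre-rescue samples, including those at 2 h and 6 h if rescue starts on Day 1.

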12.4. Determination of Sample Size

Due to the exploratory nature of the study, there is no formal statistical hypothesis. The difference between treatments for the reduction of DSA will however be presented with 95% confidence interval. A sample size of 20 implifidase and 10 PE subjects is proposed.

In two previous implifidase studies, 14-HMedIdeS-04 and 15-HMedIdeS-06, the IgG reduction for 5 days was 90% and 93% respectively. The corresponding standard deviations are 6% and 4% respectively. Assuming a similar variability in the PE treatment arm, the expected width of the 95% CI for the difference in DSA reduction will be around 8% point. This supports that 20+10 patients are appropriate. Also, the sample size is in line with experience from previous similar Phase II studies with other compounds to obtain adequate safety, tolerability and PK data to achieve the objectives of the study.

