2.2 Determination of sample size

No formal calculation has been done for the sample size. A sample size of totally 30 patients is chosen where 20 patients are treated with imlifidase and 10 patients are treated with PE.

The standard deviations for the two previous studies 14-HMedIdeS-04 and 15-HMedIdeS-06 can be considered to argue for the sample size of 30 patients. The standard deviations for the reduction of the IgG were 6% in the 14-HMedIdeS-04 and 4% in the 15-HMedIdeS-06 study. If the standard deviations are assumed to be similar in this study, it will give approximately an 8% point wide Confidence Interval (CI) when the sample size on 10+20 patients are considered. The 8% point wide of the CI is an acceptable wide and therefore the sample size on 30 patients can be used.

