4.1.1 Data presentation

No formal statistical hypothesis testing will be performed in this study.

The data will be presented descriptive and for some of the endpoints 95% confidence intervals for the treatment difference will be presented.

Numerical data will be presented in summary tables by number of patients, arithmetic mean, median, standard deviation (SD), minimum and maximum.

When numerical data are recorded at different time points, absolute values at each time point and changes from baseline may be presented in the summary tables.

Categorical data will be presented by frequency and percent of patients. Number of events will also be reported where applicable.

Summary tables will in general be presented by treatment group and total across treatment groups unless this is not appropriate for specific tables.

Data will be listed by treatment group, patient and time point (if applicable).

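### The primary 95% CI pools one variance over 20 and 10 patients, so it is too narrow if the PE arm is the more variable one; a Welch interval is a cheap improvement, though not a cure for a few poor responders on imlifidase

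*SAP*

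**What the plan says.** The primary endpoint is each patient's largest percentage fall in summed DSA MFI within 5 days. On the interval for the treatment difference, SAP 4.6.1 states: "The confidence interval for the difference in the reduction is found by using an Analysis of variance (ANOVA) model with treatment as fixed effect". SAP 2.4 sets 2:1 allocation, 20 imlifidase and 10 PE, without stratification. SAP section 8 plans the resulting table for the FAS (14.2.1) and the PPS (14.2.2).

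The one provision for a failed model assumption is: "If the normality assumption is violated, sensitivity analyses using transformations of the primary endpoint will be performed". No transformation is named, and unequal variances are not mentioned.

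Equal spread appears only in the sample-size reasoning. Protocol 12.4 reports: "In two previous implifidase studies, 14-HMedIdeS-04 and 15-HMedIdeS-06, the IgG reduction for 5 days was 90% and 93% respectively", with SDs of 6% and 4%, and continues: "Assuming a similar variability in the PE treatment arm". SAP 2.2 repeats the step: "If the standard deviations are assumed to be similar in this study". Both arrive at a CI about 8 percentage points wide.

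**The concern.** An ANOVA with treatment as its only term estimates one residual variance. The estimate is weighted towards the larger arm (19 of 28 degrees of freedom), while the smaller arm contributes more to the true variance of the difference. If the smaller arm is the more variable, the interval is too narrow.

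Nothing in the documents settles which arm varies more. A more variable PE arm is plausible: PE follows each site's own standard (Protocol 5.2) and immunoadsorption may replace it (Protocol 1.2), whereas imlifidase is one fixed dose. Reductions near the 100% ceiling also leave little room for spread. The reverse is possible too, since Protocol 1.3 allows for patients in whom imlifidase does not clear DSA adequately.

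What is at stake is the honesty of the one stated precision for the primary comparison. No hypothesis test, threshold or interim decision depends on it.

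**Working it through.** **Inputs from the documents.** n = 20 and 10 (SAP 2.4); 95% CI from a treatment-only ANOVA (SAP 4.6.1); SDs of 6% and 4% for IgG reduction on imlifidase (Protocol 12.4). **Assumptions.** The imlifidase SD is 5 points (midway between 4 and 6) unless stated otherwise. All PE SDs, all means and all shares of poor responders are assumed.

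**1. The plan's own figure.** Width = 2 × t(0.975, 28) × SD × √(1/20 + 1/10) = 2 × 2.048 × 5 × 0.387 = 7.9 points. SD 4 gives 6.3 and SD 6 gives 9.5. The 8-point width reproduces, on the premise of equal SDs.

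**2. Why it narrows.** Take a PE SD of 10 (ratio 2).
- Expected pooled variance: (19 × 25 + 9 × 100)/28 = 49.1. Times 0.15 this is 7.37, so the SE is about 2.71.
- True variance of the difference: 25/20 + 100/10 = 11.25, so the SE is 3.35.
- The ANOVA standard error is about 0.81 of what it should be.

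**3. Coverage, normal data** (200,000 simulated trials per row; pooled with 28 df, Welch with Satterthwaite df).

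| SD ratio PE : imlifidase | Pooled coverage | Welch coverage | Mean width, pooled / Welch (points) |
|---|---|---|---|
| 0.5 | 98.1% | 95.0% | 6.8 / 5.6 |
| 1 | 95.0% | 95.0% | 7.9 / 8.0 |
| 1.5 | 91.4% | 94.9% | 9.3 / 11.1 |
| 2 | 88.6% | 94.9% | 11.0 / 14.4 |
| 3 | 85.4% | 95.0% | 14.7 / 21.2 |

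Before rounding, the widths at ratio 1 are 7.86 and 8.04, a difference of about 0.2 points.

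**4. Bounded data** (beta distributions on 0–100).
- Imlifidase mean 92, SD 5; PE mean 60–80, SD ratio 1.5–3: pooled 84.4–91.3%, Welch 93.1–94.8%.
- Imlifidase the more variable arm (mean/SD 92/7.5, 92/10, 88/15; PE 70/5): pooled 96.2%, 95.9%, 96.3%; Welch 94.9%, 94.3%, 93.2%.

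**5. A few poor responders on imlifidase** (poor responders mean 40, SD 10; others mean 92, SD 5; PE mean 70). Cells are pooled / Welch coverage in %.

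| Share of poor responders | PE SD 5 | PE SD 10 | PE SD 15 |
|---|---|---|---|
| 5% | 90.8 / 90.8 | 91.9 / 94.6 | 90.8 / 94.9 |
| 10% | 90.8 / 89.8 | 93.3 / 94.1 | 93.3 / 94.9 |
| 15% | 94.9 / 91.8 | 95.0 / 93.8 | 94.8 / 94.7 |
| 20% | 96.4 / 92.7 | 96.3 / 94.1 | 95.8 / 94.8 |

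With PE SD 5 the Welch interval is also the narrower one: mean widths 12.6, 16.0, 18.7 and 20.8 points against 15.6, 21.0, 25.1 and 28.2 pooled.

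The cause is skew. At a 5% share, 0.95^20 = 36% of trials contain no poor responder among 20 patients, so they show a high mean and a small SD. Nearly all misses then place the whole interval above the true difference, in favour of imlifidase.

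Harsher versions hurt both methods. With 5% poor responders at 20–60% reduction and a PE SD one quarter of the imlifidase SD, coverage is 78% pooled and 79% Welch. With poor responders at 0–30% it is 72% and 76%.

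**The case against.** The strongest reply is that the SD ratio of 1.5 to 3 has no support in the documents. Under their own planning assumption the pooled interval covers 95.0% and there is no defect. Varying PE practice shows that procedures differ, not how far the best value within 5 days differs. If imlifidase is the more variable arm and the data are roughly normal, the pooled interval errs on the safe side. With poor responders and a tight PE arm, the proposed interval is narrower than the present one and covers no better. On this view Welch belongs beside the ANOVA interval and not in its place.

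It is also fair to say that much can already be seen. SAP 4.1.1 plans: "Numerical data will be presented in summary tables by number of patients, arithmetic mean, median, standard deviation (SD), minimum and maximum". SAP 4.6.1 adds: "The maximum reduction per patient will be listed by patient". A reader could recompute a Welch interval from that listing. A transformation might also happen to reduce unequal spread.

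The uncertainty about the ratio stands, and so does the poor-responder limit. They do not make pooling the better default. The sample-size text assumes equal spread without PE data, and the transformation analysis is triggered by non-normality, changes the scale of the difference and leaves the reported interval as it was. In the scenarios of steps 3 to 5, apart from the two harsher ones, pooled coverage runs from about 84% to 98% and Welch from about 90% to 95%. The loss from Welch in the mixtures, at most about 4 points of coverage, is smaller than the loss from pooling when PE is the more variable arm, up to about 10 points.

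**Conclusion.** The point holds as a cheap improvement. The stated 95% of the primary interval rests on an equal-variance premise for which the documents give no PE data. If the PE SD is 1.5 to 3 times the imlifidase SD, coverage falls to between about 91% and 85%; Welch restores about 95% for normal data and 93–95% for bounded data. If imlifidase is the more variable arm without marked skew, the pooled interval is merely conservative. If a few patients respond poorly to imlifidase and PE is tight, neither interval can be relied on, and Welch can be somewhat worse. The trial is descriptive, so no formal conclusion changes. The gain is a stated precision that better matches its label.

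**What to change.** In SAP 4.6.1, prespecify a CI with group-specific variances as the reported interval in Tables 14.2.1 and 14.2.2: Welch/Satterthwaite, for example PROC MIXED with a residual variance per treatment group and DDFM=SATTERTHWAITE. Keep the pooled ANOVA interval as a sensitivity analysis. In the same two tables show n, mean, SD, median, minimum and maximum of the maximum reduction for each arm, so that unequal spread or a few poor responders can be seen next to the interval.

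The cost is one or two sentences and a small code change. The interval is about 0.2 points wider if the SDs are equal, and clearly wider if PE is more variable (14.4 against 11.0 points at ratio 2). The change does not protect against outlying poor responders, which is why the per-arm statistics and the retained pooled interval are part of it.
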